4.7 Study Observation Phase (Phase 3)

During months 4-6, all three arms will be in the observation phase, in which none of the participants receive reminders, feedback, or adherence-contingent incentives.

4.8 Visit 4 (clinic or home preferred, telephone if not possible) – month 7

- Study visit 4 survey question blocks (see section 4.11.2)

4.9 Visit 5 (clinic or telephone) – month 12-13

- Study visit 5 survey question blocks (see section 4.11.2)

4.10 Subject Completion/Withdrawal

Because the study intervention is dependent on functioning cellphone-sensor-platform data connection, subjects for whom the research staff cannot establish a functional adherence data feed and two-way text message communication within two weeks of enrollment will not be randomized by study staff. Specifically, these “non-responders”, for whom no electronic adherence data is transmitted and do not reply to any of the 4 text messages sent during the first two weeks of the Run-in Phase, will not undergo randomization and enter into the Experiment or Observation Phases. This criteria for randomization will be explicitly stated in the study informed consent form. Participants will be informed that their data from the Electronic Health Record can still be accessed and used as part of this research and data collection until the study ends. In order to take back this permission, participants must inform the study team of their wish to withdraw from the study.

Additionally, subjects may withdraw from the study at any time. They may also be discontinued from the study at the discretion of the Principal Investigator for inappropriate or threatening behavior with study staff.

4.10.1 Early Termination Study Visit

Subjects who withdraw from the study will have all procedures enumerated for Visit 1, 2, 3 or 4 as the early termination visit. Participants who withdraw from the study prior to completion will have the option to have their earlier responses redacted from the database. If

participants choose this option, any data collected in study visits 1-4 will be excluded from subsequent analysis.

4.11 Screening and Monitoring Evaluations and Measurements

4.11.1 Medical Record Review

Variables to be abstracted from the medical chart:

- Child sex
- Date of birth
- Weight and height
- Date of qualifying hospital admission and discharge
- Asthma severity
- Last spirometry result and date of assessment (if reported)
- Name and dose of current asthma medications (both controllers and rescue)
- Number of prescriptions and refills in the prior year for each asthma medication
- Number and date of ED visits, hospitalizations, and oral steroid courses for asthma in the preceding year
- Number and date of ED visits, hospitalizations, and oral steroid courses for asthma during the 13-month study period

4.11.2 Other Evaluations, Measures

The following instruments (or question blocks from the following instruments) will be used to assess key constructs at each study visit:

- Child and parent self-efficacy, measured using the Child and Parent Asthma Management Self Efficacy scale¹⁸,
- Parent/child responsibility for asthma care measured using the Asthma Responsibility Questionnaire¹⁹,
- ICS habit strength, measured using the Habit Strength Index adapted for asthma controller use²⁰.

4.12 Efficacy Evaluations

We will collect a number of efficacy outcomes including parent reported asthma control and use of prescribed medicine over the study interval.

4.12.1 Diagnostic Tests, Scales, Measures, etc.

- Child Asthma Control Tool (cACT)
- Daily Medication adherence – calculated as the mean daily proportion of prescribed doses taken by study month. Days that reflect >1 will be truncated to 1.

4.13 Safety Evaluation

Subject safety will be monitored by adverse events.

4.14 Primary Endpoint

The primary outcome will be adherence to ICS regimen both during the *Experiment* interval (months 1-3). Adherence over these study intervals will be characterized as a daily observed-to-prescribed ICS adherence proportion averaged by study month. To operationalize this, a daily medication use log composed of 180 sequential ICS use observations will be generated, representing the count of ICS doses taken each day of study enrollment. These daily counts will be converted into proportions by dividing by the daily prescribed dose and imposing an upper limit of 1 in order to prevent doses taken above the prescribed limit – either during the use of flare plans or attempted “gaming” of the incentives by the participants – from influencing interval adherence estimates. Observed actuations will be quantified using electronic sensors.

4.15 Secondary Endpoints

Secondary endpoints will include the following:

- Adherence to ICS regimen in *Observation* interval (months 4-6)
- Adherence trajectory, as determined by group-based modeling of adherence patterns.
- Change in cACT score from first study visit to the second, third, fourth, and fifth study visits.
- Number of asthma-related emergency room visits, hospitalizations, and oral steroid courses between study conditions.
- Healthcare costs associated with emergency room visits, hospitalizations, and oral steroid courses between study conditions.
- Continued use of sensors in 7-13 month follow-up period (feasibility outcome)

Health system use outcomes will be assessed primarily using CHOP electronic health record data and, secondarily, via caregiver report to account for utilization that may have occurred outside of CHOP. ED visits, hospitalizations, and oral steroids courses will be characterized as asthma-specific using existing, validated asthma registry definitions that include asthma visit diagnoses, medication orders, and asthma pathway order set activation. Costs will be estimated using average insurance payments for asthma ED visits, hospitalizations, and oral steroid courses in addition to the costs of the intervention components (i.e. sensors, incentive value, and research staff support).

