- 2) Assess proposed mechanisms by which intervention strategy influenced adherence trajectory, including (1) participant self-efficacy, (2) medication responsibility, and (3) habit formation.
- 3) Explore caregiver and child perceptions of acceptability of intervention components and how they influenced adherence trajectory.

Study Design:

Basic design: Randomized controlled trial

Setting/Participants:

To accomplish the above objectives, we propose to enroll 125 children and their parents in a six-month intervention with a six-month follow-up period. Children will be ages 5-12, and must have two or more visits to any combination of the outpatient, ED or hospital setting in the past year for asthma exacerbations at Children's Hospital of Philadelphia.

Study Interventions and Measures:

[figure not shown]
The study intervention will include daily automated medication reminders (either via text message or push reminder), an app to track daily medication use, and nominal incentives to promote daily controller use. Inhaled controller medication adherence and rescue medication use will be measured using electronic monitors affixed to the inhalers. Factors associated with differential adherence will be assessed using surveys administered during enrollment, the experiment interval (months 2 and 4), the observation interval (month 7), and study completion (months 12-13). Efficacy outcomes will include change in parent-reported asthma control and mean adherence to ICS between study arms during the experiment interval, as well as the observation interval.

TABLE 1: SCHEDULE OF STUDY PROCEDURES

Study Phase	Screening and initial survey	Run-in period	Study survey	Experiment period			Study survey	Observation period	Study survey	Study completion survey
Visit Number	1 (clinic/hospital/phone)		2 (clinic/phone)				3 (clinic/phone)		4 (clinic/home phone)	5 (clinic/phone)
Arms	1,2,3	1,2,3	1,2,3	1	2	3	1,2,3	1,2,3	1,2,3	1,2,3
Study Month	0	0	2	1-3			4	4-6	7	12-13
Informed Consent/Assent	X									
Review Inclusion/Exclusion Criteria	X									
Demographics/Medical History	X									
Prior/Concomitant Medications	X									
Dispense Electronic Monitors	X									
Questionnaires	X		X				X		X	X
Child asthma control tool	X		X				X		X	X
Electronic monitoring		X		X	X	X		X	X	X
Daily medication reminders				X	X					
Adherence incentives				X						

FIGURE 1: STUDY DIAGRAM

A flow diagram of the study is included below.

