3.1.1 Screening Phase

Potential subjects will be screened through the daily census listings for the inpatient units on the Epic medical record at CHOP using the protocol inclusion and exclusion criteria. Epic alerts and patient lists identifying high risk children with asthma will assist research staff in screening potential subjects.

Eligible children and their caregivers will be recruited during an asthma hospital admission, whenever possible, or in the month following hospital discharge, if the study team is unable to reach the family during the hospitalization. In the latter circumstance or if the child is eligible through asthma related outpatient visits, the study team will contact eligible participants by phone and if the caregiver expresses interest, the study team will approach the caregiver and child for informed consent/assent at a follow-up visit or via phone, if in-person recruitment is not feasible.

Parental/guardian permission (informed consent) and, if applicable, child assent, will be written on a physical copy of the consent form, when consent/enrollment takes place in person, prior to any study related procedures being performed. In the circumstance of telephonic enrollment, electronic consent via the REDCap platform will be obtained prior to any study related procedures.

If subjects consent to enrollment, the Study Run-in Phase will begin on the day of enrollment.

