3.1.2 Run-in Phase (Month 0)

The study will be broken down into three discrete phases: (1) *Run-in* (2) *Experiment*, and (3) *Observation* (Figure 2). During the *Run-in* phase, every caregiver-child dyad will have access to the inhaler sensor app and will receive electronic ICS use monitoring. ICS use will be monitored using an electronic sensor that affixes to their ICS inhaler and will remain through the study *Observation* phase. Participants will be sent 4 text messages, each designed to elicit a response from the caregiver about the study technology or the study itself. (See Appendix 1 for content of the Run-in text messages) Participants for whom any inhaler use data is transmitted to the study platform within the first 2 weeks of the Run-in Phase AND reply to one or more of the 4 text messages sent from the study platform (“Responders”) will be randomized into one of three arms at the end of the Run-in phase. (see section 4.10 for details on procedures for “Non-responders”) The second two weeks of the Run-in Phase is designed to provide baseline adherence data.

[figure not shown]

Figure 2: Study schema for proposed RCT

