4.16.2 Efficacy Analysis

We will assess the effectiveness of randomization by comparing the study arm balance on key demographic, clinical, and past health care utilization variables using analysis of variance (ANOVA) and t-tests or the nonparametric equivalent for continuous variables and chi-square tests or Fisher exact tests for categorical variables.

Primary analysis: Our primary outcome will be monthly ICS adherence in months 0-3 (Experiment Phase). Secondary outcomes will include monthly ICS adherence in months 4-6 (Observation Phase), asthma control at the end of the Experiment and Observation period. Secondary outcomes will also include monthly ICS adherence in months 7-13 (follow up period) to assess feasibility and acceptability of longer durations of electronic monitoring. We will consider arcsine transformation on the ICS adherence outcomes as necessary. This technique is commonly used for proportion data. We will use generalized estimating equations (GEE) to adjust for within-subject correlations due to repeated measures for the study's primary and secondary monthly adherence outcomes. Models will include main effects for arm and time (month) and arm-by-month interaction terms to allow for differing ICS adherence over time between arms. The dependent variable of monthly ICS adherence will be defined as mean daily observed-to-prescribed ICS actuation proportion for each study month. Mean daily adherence proportion will be capped at 1, such that participants taking more than their prescribed daily dose cannot receive "extra credit" for doses taken on those days. All statistical tests will be 2-sided. A P-value <0.05 will be considered statistically significant.

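### No analysis is named for cACT, Sections 4.15 and 4.16.2 define the outcome differently, and Visit 1 cACT is not planned as a covariate

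*Combined protocol and SAP*

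**What the plan says.** Section 4.15 gives the endpoint as "Change in cACT score from first study visit to the second, third, fourth, and fifth study visits", which is four changes. The abstract also speaks of change: "Efficacy outcomes will include change in parent-reported asthma control and mean adherence to ICS between study arms", over the Experiment and Observation intervals. Section 4.16.2 lists "asthma control at the end of the Experiment and Observation period", which is two time points and is not worded as change.

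The only repeated-measures model in the plan is the GEE in Section 4.16.2. Its stated purpose is to "adjust for within-subject correlations due to repeated measures for the study's primary and secondary monthly adherence outcomes", so cACT lies outside it. Its terms are given as "Models will include main effects for arm and time (month) and arm-by-month interaction terms", with no baseline term. Covariate adjustment is mentioned for the trajectory and hazard models, but not for cACT.

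Table 1 marks the row "Child asthma control tool" at month 0 and at each of the four later survey visits. Under Section 3.1.2, participants who meet the run-in criteria "will be randomized into one of three arms at the end of the Run-in phase", so Visit 1 cACT precedes randomization. Section 7.1.1 opens by placing assignment at enrollment, but the same section later agrees with 3.1.2. Section 4.4 adds that families do not learn their arm until the Experiment phase.

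**The concern.** A reader of Section 4.15 alone would probably subtract Visit 1 from each later score and compare the arms four times. A reader of Section 4.16.2 alone could compare raw scores at two visits. Neither section mentions adjusting for the baseline value, so the choice stays open until data are in hand.

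Visit 1 may also be an unusual measurement. Section 3.1.1 says "Eligible children and their caregivers will be recruited during an asthma hospital admission, whenever possible". Other children join in the month after discharge, or by phone after outpatient visits. Baseline control is therefore taken at varying distances from an exacerbation and may predict later control only loosely. A change score does worst in that setting, because it subtracts the whole baseline value whether or not that value is informative.

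At stake are the width of the intervals for cACT and the clarity of which cACT result is the reported one.

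**Working it through.** **Inputs.** The documents give no figure for cACT, so its SD and the baseline-to-follow-up correlation r are assumptions here. The number per arm comes from Section 4.17, for the adherence comparison of arms 1 and 3. That figure reproduces with the unpooled two-proportion formula: (1.960 + 0.842)² × 2 × 0.65 × 0.35 / 0.30² = 39.7, so 40 per arm. Then 40 / 0.8 = 50, and 50 + 25 + 50 = 125. I use 40 evaluable per arm below.

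**Equal SDs.** In units of the squared SD, the per-child variance is 2(1 − r) for change, 1 for unadjusted follow-up and 1 − r² for follow-up adjusted for baseline (ANCOVA). The ratios are (1 + r)/2 against change and 1 − r² against follow-up.

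| r | change | follow-up | ANCOVA | ANCOVA / change | ANCOVA / follow-up |
|---|---|---|---|---|---|
| 0.3 | 1.40 | 1.00 | 0.91 | 0.65 | 0.91 |
| 0.5 | 1.00 | 1.00 | 0.75 | 0.75 | 0.75 |
| 0.7 | 0.60 | 1.00 | 0.51 | 0.85 | 0.51 |

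The covariate costs one degree of freedom. With 80 children the variance factor is about 1 + 1/76 = 1.013, which moves the ratios against change to 0.66, 0.76 and 0.86. A simulation of 20,000 trials at each r gave 0.65, 0.76 and 0.86. Both estimators returned the assumed 0.5 SD effect without bias.

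**What this means at 40 per arm.** The difference detectable with 80% power is (1.960 + 0.842) × √(2 × variance / 40), in SD of cACT:

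- r = 0.3: 0.74 with change, 0.60 with ANCOVA.
- r = 0.5: 0.63 with change, 0.54 with ANCOVA.
- r = 0.7: 0.49 with change, 0.45 with ANCOVA.
- Unadjusted follow-up: 0.63 at any r.

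ANCOVA with about 26, 30 or 34 children per arm (40 × the ratio) matches unadjusted change with 40.

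**Unequal SDs.** Let s be the baseline SD divided by the follow-up SD. The change variance is 1 + s² − 2rs = (1 − r²) + (s − r)². Before the degree-of-freedom cost it is therefore never below the ANCOVA variance, and the two are equal when s = r. At s = 1.25 and r = 0.3 the ratio is 0.91 / 1.8125 = 0.50. At s = 0.8 and r = 0.7 it is 0.51 / 0.52 = 0.98.

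**Chance imbalance.** With 40 against 40, the standard error of the baseline mean difference is √(2/40) = 0.22 SD. With equal SDs, about (1 − r) of any such difference carries into a change-score comparison: 0.7, 0.5 or 0.3 of it at r = 0.3, 0.5 or 0.7. Under randomization this widens the interval and does not bias the estimate.

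**Change as the outcome.** ANCOVA on change and ANCOVA on follow-up, each with baseline as covariate, gave the same arm effect in the simulated data. Section 4.15 can keep its endpoint if baseline enters the model.

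**The case against.** The strongest objection is that Section 4.15 is a list of endpoints. It names a variable and no estimator. A reader might infer that the plan commits to four raw, unadjusted change comparisons, but no passage says so, and a change endpoint is compatible with baseline adjustment. This stands: the fault is that the analysis is unspecified and no adjustment is planned.

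The choice of comparator also matters. If Section 4.16.2 means raw follow-up scores, the gain from adjustment at r = 0.3 is 9%, not 35%. This stands, and both comparators are therefore shown.

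The argument for a weak correlation is conjecture. Recruitment during admission is preferred, but Sections 3.1.1, 3.4.1 and 4.2 allow other routes, and no passage gives the share enrolled in hospital. This also stands, so r is given as a range.

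Finally, Section 4.17 disclaims power for health outcomes. That limits how much the point matters, but it does not favor a less precise analysis of data already collected.

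**Conclusion.** The point holds as one of specification and precision. Two sections describe the cACT outcome differently, no model is named, and a pre-randomization covariate that is already collected has no planned use. Under equal SDs and r from 0.3 to 0.7, adjustment removes 35% to 15% of the change-score variance, or 9% to 49% of the unadjusted follow-up variance. If the SDs differ, the gain over change could be as large as half (s = 1.25, r = 0.3) or almost nothing (s = 0.8, r = 0.7). The documents cannot settle where in that range the trial lies.

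Two stronger readings are not supported. One is that cACT is the trial's main health outcome: Section 4.15 does not rank its endpoints, and Section 2.1 names healthcare use and costs as the secondary outcomes. The other is that the cACT effect is meant to power the later multicenter study: Section 4.17 refers there to intervention components and utilization, and does not mention cACT.

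**What to change.** In Section 4.16.2, specify one repeated-measures model for cACT at Visits 2 to 5, with Visit 1 cACT as covariate plus arm, visit and arm-by-visit terms. Name the baseline-adjusted arm differences at Visit 3 (month 4) and Visit 4 (month 7) as the main cACT results. These visits match the ends of the Experiment and Observation phases, so Sections 4.15 and 4.16.2 then agree. Visits 2 and 5 stay in the model as supporting results, and change scores stay as descriptive summaries.

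The cost is SAP wording and about one degree of freedom. No new data are needed.

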3.4 Study Population

3.4.1 Inclusion Criteria

- 1) Males or females age 5 to 12 years and their parent or legal guardian.
- 2) Caregiver has an app enabled cellular phone (i.e., smartphone)
- 3) Prescribed inhaled corticosteroid or corticosteroid/long acting beta agonist combination for daily use
- 4) At least 2 asthma exacerbations in the preceding year (Any combination of hospitalizations, ED visits, or outpatient visits where oral steroid courses were administered for asthma)
- 5) Parental/guardian permission (informed consent) and if appropriate, child assent.

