4.17 Sample Size and Power

Our analysis of pilot data demonstrates a 48% difference in ICS adherence when comparing a time interval with financial incentives (the same schema proposed in this study) to a time period without incentives. To ensure a power of 80% at a significance level of 0.05 to detect a more conservative 30% difference in average adherence between arms 1 and 3 in the *Experiment* phase (corresponding to 65% and 35%, respectively), 40 patients are required in each of these two arms. To ensure scientific rigor given the vulnerable nature of the population, we estimate ~20% loss to follow-up. Therefore, we will aim to enroll 50 participants in study arms 1 and 3 and 25 participants in arm 2, or 125 participants total, to achieve sufficient power to detect a difference between arms 1 and 3. The study is not to be powered to detect differences in arms 1 to 2 or 2 to 3 (hence the 2:1:2 randomization schema) or for health outcomes or cost offset; rather, it is intended to obtain preliminary estimates of marginal effects of the intervention components and effect sizes on utilization outcomes by comparing arm 1 to 2 and 2 to 3 to power a future multicenter study. Baseline data reveals that ~50% of children with at least 2 prior hospitalizations have a repeat ED visit or inpatient stay 6 months after the 2nd hospital discharge.

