4.18 Additional analyses

Hypothesis 1.2 Longer time intervals to next asthma-related ED or inpatient visit, and reduced healthcare use and costs, will be observed in Arm 1 compared to Arms 2 and 3 (and in Arm 2 compared to Arm 3).

Time to next asthma-related ED or inpatient visit from enrollment will be first modeled using the Kaplan-Meier plots. Study arms will be compared using log-rank tests and unadjusted Cox proportion hazards models. Adjusted hazard models will include the additional covariates described above and the Anderson-Gill method will be used to account for recurrent events. Total medical costs will be estimated for the 12 months following study enrollment, accounting for each asthma-related ED visit and hospitalization, as well as the expenses incurred with study participant incentives, sensors, and use of the WTH automated platform. We predict that intervention will reduce medical costs, thereby contributing to a *cost offset*. We will estimate potential savings in medical costs by calculating the difference in average total medical costs minus study-related expenses between study arms.

Aim 2. Assess proposed mechanisms by which intervention strategy influenced adherence trajectory.

Aim overview: The broad goal of this aim is to assess which participant and study characteristics are associated with different longitudinal adherence trajectories.

Characteristics to be examined include baseline factors (demographic, clinical, and prior health utilization factors), intervention strategy (study arm), and potentially modifiable behavioral characteristics. Of specific interest is how intervention strategy in the Experiment phase (study arm) influences child asthma self-efficacy, shared medication responsibility, and medication habit over time and how these characteristics vary with longitudinal ICS adherence trajectories. [Figure 4]

Hypothesis 2: Increases in (1) participant self-efficacy, (2) shared medication responsibility, and (3) habit score will partially mediate the relationship between study arm and sustained adherence trajectory.

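### Costs are compared without adjustment and the utilization counts have no stated adjustment, although prior-year counts of the same events are abstracted; the covariates of the planned adjusted hazard models are not listed

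*Combined protocol and SAP*

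**What the plan says.** - **Endpoints (4.15).** The utilization endpoint is "Number of asthma-related emergency room visits, hospitalizations, and oral steroid courses between study conditions", and the cost endpoint is "Healthcare costs associated with emergency room visits, hospitalizations, and oral steroid courses between study conditions". Neither has a model or a covariate there.
- **Baseline of the same events (4.11.1).** The chart review abstracts "Number and date of ED visits, hospitalizations, and oral steroid courses for asthma in the preceding year".
- **Eligibility (3.4.1).** Entry requires "At least 2 asthma exacerbations in the preceding year", so the prior-year total starts at 2.
- **Balance check (4.16.2).** The plan includes "comparing the study arm balance on key demographic, clinical, and past health care utilization variables". It states no consequence if imbalance is found.
- **ED and inpatient events (4.18, Hypothesis 1.2).** After Kaplan-Meier plots, log-rank tests and unadjusted Cox models, the plan adds: "Adjusted hazard models will include the additional covariates described above and the Anderson-Gill method will be used to account for recurrent events".
- **Costs (4.18).** Savings are estimated by "calculating the difference in average total medical costs minus study-related expenses between study arms".
- **Aim 2 (4.18).** Prior utilization is also a candidate baseline factor in the trajectory-group regressions. This aim cites a section on covariates that is not in the text available.
- **Purpose (4.17).** The study is not powered for health outcomes or cost offset. It is meant to "obtain preliminary estimates of marginal effects of the intervention components and effect sizes on utilization outcomes", in order to power a later multicenter study.

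**The concern.** A child's asthma events in the past year are the natural baseline for asthma events in the next, and the trial already collects them. For two outcomes the plan does not say that it will use them. The cost contrast is explicitly a difference of averages, and oral steroid courses have no analysis model at all. For ED visits and hospitalizations an adjusted model is planned, but its covariates cannot be identified from the text.

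Section 4.17 gives these estimates one job, which is to supply effect sizes for the next trial. Precision matters for that job even though significance does not. With arms of 50, 25 and 50 and variable event counts, part of any chance difference in prior utilization carries into an unadjusted estimate and into the projected cost offset. An unlisted covariate set also leaves the choice of covariates open until outcomes are known.

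**Working it through.** **1. The plan's own figure.** The only sizing is for adherence, 65% versus 35%, two-sided 0.05, 80% power. With unpooled variance, n = (1.960 + 0.842)² × (0.65×0.35 + 0.35×0.65) / 0.30² = 7.849 × 0.455 / 0.09 = 39.7, so 40 per arm. Then 40/0.80 = 50, and 50 + 25 + 50 = 125. This reproduces 4.17. It does not involve utilization, so nothing below changes it.

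**2. Which outcomes lack adjustment.**

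| Outcome | Stated analysis | Prior-year count used? |
|---|---|---|
| Costs | Difference in arm averages (4.18) | No |
| Oral steroid courses | None beyond listing (4.15) | Not stated |
| ED visits, hospitalizations, as counts | None beyond listing (4.15) | Not stated |
| ED or inpatient events, time to event and recurrent | Unadjusted, then adjusted Cox and Andersen-Gill (4.18) | Unclear, covariates not listed |

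**3. Gain from adjustment.** In a linear model, adjusting for a baseline that correlates r with the outcome multiplies the variance of the arm contrast by 1 − r² and the interval width by √(1 − r²). The documents give no r, so these values are assumptions.

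| r | Variance × | CI width × | 50 per arm acts like |
|---|---|---|---|
| 0.15 | 0.978 | 0.989 | 50/0.978 = 51 |
| 0.2 | 0.96 | 0.980 | 52 |
| 0.3 | 0.91 | 0.954 | 55 |
| 0.4 | 0.84 | 0.917 | 60 |
| 0.5 | 0.75 | 0.866 | 67 |

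**4. Which r is plausible.** A gamma-Poisson model was simulated with entry limited to 2 or more prior-year events. Section 4.17 says about 50% of children with at least 2 prior hospitalizations have a repeat ED visit or inpatient stay within 6 months. Four settings lay near that figure:

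| Gamma shape, population mean | Any event in 6 months | r at 12 months | Variance reduction (r²) |
|---|---|---|---|
| 4, 1.0 | 46% | 0.14 | 1.9% |
| 2, 1.0 | 51% | 0.24 | 5.7% |
| 0.5, 0.5 | 50% | 0.36 | 13.1% |
| 1, 1.0 | 57% | 0.38 | 14.3% |

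This supports a working range of about 0.15 to 0.4. Values above 0.5 appeared only with more events and strong heterogeneity (shape 1, mean 2.0: 72% with an event, r = 0.57). Adding steroid courses raises the event frequency, but the documents do not say by how much.

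**5. Check in a count model.** Two simulations fitted robust Poisson models and measured the variance of the log rate ratio.
- 50 versus 50, assumed rate ratio 0.7, 45% to 56% with a 6-month event: r was 0.17 to 0.33 and the variance fell 0% to 7%. The linear formula predicts 0.17² = 3% to 0.33² = 11%.
- 40 versus 40, assumed rate ratio 0.5: r was 0.33 to 0.55 and the variance fell 6% to 28%. The formula predicts 11% to 0.55² = 30%.

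The formula is therefore somewhat generous for count models.

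**6. Chance imbalance.** In baseline SD units, the standard error of the difference in mean prior count is √(1/n₁ + 1/n₂). This is √(1/50 + 1/50) = 0.20 for arm 1 versus arm 3, and √(1/25 + 1/50) = 0.24 for comparisons with arm 2. A one-standard-error imbalance of 0.20 at r = 0.4 shifts the unadjusted estimate by 0.4 × 0.20 = 0.08 outcome SD. The contrast's own standard error is 0.20 outcome SD, and (0.08/0.20)² = 0.16, which is the r² in step 3.

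**The case against.** The strongest reply is that much of this is already in hand. Section 4.18 plans adjusted and recurrent-event models for ED and inpatient events. The back-reference may well point to the demographic, clinical and past-utilization variables of 4.16.2, the only such set named earlier. Section 4.15 lists endpoints and need not specify models. The study disclaims power for these outcomes, the balance comparison would reveal an imbalance, and entry at 2 or more events narrows the baseline range and so limits the gain.

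Most of this stands. A reader might infer that no utilization outcome is adjusted, or that past utilization serves only as a balance check. The documents do not support either: 4.18 plans adjusted hazard models, and Aim 2 enters prior utilization in the trajectory regressions. A reader might also infer bias, but randomization keeps the unadjusted contrasts unbiased.

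The choice of count model is partly preference. Covariates in a Cox model also change what the hazard ratio estimates, which is a reason to keep the unadjusted results too.

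The reply does not reach costs, which are explicitly unadjusted, or steroid courses, for which no analysis is given. A balance test reports an imbalance without removing its effect. And a back-reference that needs guessing is not a pre-specified covariate list.

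**Conclusion.** The point holds in a limited form. Adjustment for prior-year events is absent from the cost contrast and unstated for the counts, most clearly for oral steroid courses. For ED and inpatient events the fault is an unidentified covariate list; the documents do not show that adjustment is missing.

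The gain is probably modest: about 2% to 16% less variance and 1% to 8% narrower intervals at an assumed r of 0.15 to 0.4, and possibly less in a count model. Reductions of 25% and 13% need r = 0.5, hence events that are more frequent or more heterogeneous than the documents establish. For costs, r is that between prior-year and follow-up cost and is equally unknown. Quoting a large power gain would go beyond the documents, both because r is assumed and because 4.17 claims no power for these outcomes.

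The benefit is precision and protection against chance imbalance, on secondary estimates intended to size a later trial.

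**What to change.** In 4.15 and 4.18:

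1. Analyse event counts, including oral steroid courses, with a rate model (for example Poisson with robust variance) containing arm, log prior-year count of asthma events and a follow-up-time offset. The log of the total count always exists, because eligibility sets it at 2 or more.
2. Adjust the cost difference for prior-year utilization, computed as prior-year counts times the same average payments used for follow-up costs.
3. List the covariates of the adjusted Cox and Andersen-Gill models in place of the back-reference, and name the prior-year count among them.
4. Report the planned unadjusted results alongside.

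The cost is wording and one extra model term per analysis. It needs no new data, visits or participants, because the prior-year counts are already abstracted. The list should be fixed before outcomes are examined by arm.
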